## 7.4.2 Modification of Study Therapy

## 7.4.2.1 Dose Delays

**Table 7.4.2.1-1: Dose Delays** 

	Ipilimumab	Nivolumab 3 mg/kg (a)	Nivolumab 240 mg (b)	Fluorouracil	Cisplatin
Specifications p	er Protocol				
Dose considered as actually delayed	If the delay is exceeding 5 days	If the delay is exceeding 3 days			
Maximum delay allowed between doses	12 weeks	8 weeks	8 weeks	8 weeks	8 weeks
Definitions for	Definitions for the Analysis				
Dose Delay	duration of preceding cycle in days – 42	duration of preceding cycle in days – 14	duration of preceding cycle in days – 14	duration of preceding cycle in days – 28	duration of preceding cycle in days – 28
Categories of dose delays	on-time, 4 - 7 days, 8 - 14 days, 15 - 42 days, 42 - 56 days, > 56 days	on-time, 4 - 7 days, 8 - 14 days, 15 - 42 days, 42 - 56 days, > 56 days	on-time, 4 - 7 days, 8 - 14 days, 15 - 42 days, 42 - 56 days, > 56 days	on-time, 4 - 7 days, 8 - 14 days, 15 - 42 days, 42 - 56 days, > 56 days	on-time, 4 - 7 days, 8 - 14 days, 15 - 42 days, 42 - 56 days, > 56 days
(a) N+I arm (b) N+C arm					

The following parameters will be summarized by treatment arm:

• Number of dose delayed per subject, Length of Delay and Reason for Dose Delay.

Reason for dose delay will be retrieved from CRF dosing pages.

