Treatment Group	Drug Name	Cycle 1 (Week 1)	Cycle 2a (Week 3)	Cycle 3a (Week 5)	Cycle 4a (Week 7)	Cycle 5a (Week 9)	Cycle 6a (Week 11) till EOT
Nivolumab + Ipilimumab	Nivolumab 3 mg/kg	Day 1	Day 1	Day 1	Day 1	Day 1	Day 1
	Ipilimumab b 1 mg/kg	Day 1			Day 1		

a Cycle 2 till EOT: Subsequent nivolumab doses may be administered within 3 days before or after the scheduled date if necessary. There should be no less than 12 days between doses.

b Ipilimumab dose is administered Q6W, within 5 days before or after the scheduled date if necessary. There should be no less than 37 days between ipilimumab doses.

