- Any treatment delay resulting in an interruption in nivolumab dosing > 8 weeks, or interruption in ipilimumab > 12 weeks, with the following exceptions:
  - Dosing delays to allow for prolonged steroid tapers to manage drug-related AEs are allowed.
  - Dosing delays lasting >8 weeks for nivolumab and >12 weeks for ipilimumab from the previous dose that occur for non-drug-related reasons may be allowed if approved by the BMS medical monitor.

Prior to re-initiating treatment in a subject with a dosing delay lasting > 8 weeks, the BMS medical monitor must be consulted. Tumor assessments should continue as per protocol even if dosing is delayed. Periodic study visits to assess safety and laboratory studies should also continue every 6 weeks or more frequently if clinically indicated during such dosing delays.

Any AE, laboratory abnormality, or intercurrent illness which, in the judgment of the Investigator, presents a substantial clinical risk to the subject with continued nivolumab dosing.

The assessment for discontinuation of ipilimumab should be made separately from the assessment made for discontinuation of nivolumab. Although there is overlap among the discontinuation criteria, if discontinuation criteria are met for ipilimumab but not for nivolumab, treatment with nivolumab may continue if ipilimumab is discontinued.

In nivolumab plus ipilimumab combination treatment (Arm A), if a subject meets the criteria for discontinuation of ipilimumab but not nivolumab, treatment with nivolumab may not resume until the AE has fully resolved and the subject has discontinued steroids, if they were required for treatment of the AE. The relationship to ipilimumab should be well documented in the source documents. Nivolumab should be resumed at a dose of 3 mg/kg every 2 weeks.

If a subject meets the criteria for discontinuation of nivolumab but not for ipilimumab, both nivolumab and ipilimumab must be discontinued due to the lack of clinical efficacy of ipilimumab monotherapy (Section 1.1.6).

If a subject in the nivolumab and ipilimumab combination arm (Arm A) meets criteria for discontinuation and investigator is unable to determine whether the event is related to both or one study drug, the subject should discontinue both nivolumab and ipilimumab and be taken off the treatment phase of the study.

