Table 5.1-2: On-treatment Assessments - Subjects in Nivolumab 3 mg/kg and Ipilimumab 1 mg/kg - Arm A in CA209648			
Procedure	Cycle 1 (2 Weeks Cycle) Day 1	Each Subsequent Cycle Day 1	Note  A cycle refers to nivolumab every 2 weeks
Study Drug			
Dispense Study Treatment	X	X	
First dose to be administered within 3 calendar days after randomization. Nivolumab 3 mg/kg and ipilimumab 1 mg/kg doses may be administered within 5 days before or after the scheduled date if necessary. Interval between ipilimumab doses should not be less than 37 days and 12 days in between nivolumab doses.
 
Every 3 cycles, Ipilimumab 1 mg/kg is administered.
 
Vials may be assigned up to 3 calendar days prior to every dose date.

Some of the assessments referred to in this section may not be captured as data in the eCRF. They are intended to be used as safety monitoring by the treating physician. Additional testing or assessments may be performed as clinically necessary or where required by institutional or local regulations.

Table 5.1-3: On-Treatment Assessments - Subjects in Nivolumab 240 mg Combined with Fluorouracil plus Cisplatin - Arm B in CA209648					
Procedure	Cycle 1 Day 1	Cycle 1 Day 15	Cycles 2 and beyond Day 1	Cycles 2 and beyond Day 15	Note A cycle (4 weeks) refers to the nivolumab Q2W + FP Q4W
Safety Assessments					
Physical Examination	X	X	X	X	To be performed within 72 hours of nivolumab dosing Including audiometric assessment if required as per local standards of care.
Vital Signs	X	X	X	X	Obtain vital signs within 72 hours prior to nivolumab dose. Including BP, HR, and temperature.
Weight, BSA and ECOG Performance Status	X	X	X	X	Within 72 hours prior to nivolumab dosing See protocol appendices for ECOG Performance Status scale
Adverse Events Assessment	Continuously				Assessed using NCI CTCAE v. 4
Serious Adverse Event (SAE)	Continuously				Assessed using NCI CTCAE v. 4
Review of concomitant medications	X	X	X	X	

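### The single set of delay classes in SAP Table 7.4.2.1-1 conflicts with the table's own ipilimumab rule, overlaps at day 42, and hides the 8-week limit for fluorouracil and cisplatin

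*SAP*

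**What the plan says.** SAP Section 7.4.2.1 has one table with a column for each of ipilimumab, nivolumab 3 mg/kg, nivolumab 240 mg, fluorouracil and cisplatin.

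- **When a dose counts as delayed.** Ipilimumab: "If the delay is exceeding 5 days". The other four columns: "If the delay is exceeding 3 days".
- **How delay is measured.** For ipilimumab it is "duration of preceding cycle in days – 42". The nivolumab columns subtract 14, and fluorouracil and cisplatin subtract 28.
- **Maximum.** The table gives 12 weeks for ipilimumab and 8 weeks for the rest, and calls this a maximum delay.
- **Classes, identical in every column.** "on-time, 4 - 7 days, 8 - 14 days, 15 - 42 days, 42 - 56 days, > 56 days".

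The protocol measures the 8- and 12-week limits from the last dose given. Section 4.5.5.1 refers to "Dosing delays lasting >8 weeks for nivolumab and >12 weeks for ipilimumab from the previous dose", and Section 4.5.5.2 sets the chemotherapy limit at 8 weeks, also from the previous dose.

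On dosing windows, the footnotes to protocol Table 4.5.1.1-1 allow ipilimumab 5 days either way. For Arm A nivolumab they say: "Subsequent nivolumab doses may be administered within 3 days before or after the scheduled date if necessary". Protocol Table 5.1-2 says instead: "Nivolumab 3 mg/kg and ipilimumab 1 mg/kg doses may be administered within 5 days before or after the scheduled date if necessary".

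**The concern.** One class list is applied to drugs with different windows, different dosing intervals and different limits. A class list should follow from the definitions above it, so that two programmers working from the table produce the same counts. Here the ipilimumab rule and the ipilimumab classes disagree about the same dose. The number of delayed doses and the length of delay, both of which Section 7.4.2.1 summarises, could then contradict each other for one subject. Small shifts of this kind are foreseen: protocol Section 4.5.2.1 lets dosing days move within the 5-day window to keep ipilimumab and nivolumab synchronised.

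The table also prints a maximum taken from the protocol. A reader would expect the classes to show how many doses went past it. What is at stake is the accuracy of a descriptive exposure summary that describes three open-label regimens.

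**Working it through.** **Inputs.** Thresholds, subtracted days and classes come from SAP Table 7.4.2.1-1. The limits come from protocol Sections 4.5.5.1 and 4.5.5.2: 12 weeks = 84 days for ipilimumab and 8 weeks = 56 days for the others, counted from the previous dose.

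**Formulas.** First delayed day = SAP threshold + 1. Protocol limit on the SAP's delay scale = maximum interval − days subtracted.

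| Column | First delayed day | Limit as a delay | Where the limit falls |
|---|---|---|---|
| Ipilimumab | 5 + 1 = 6 | 84 − 42 = 42 | at the printed 42-day cut |
| Nivolumab (both) | 3 + 1 = 4 | 56 − 14 = 42 | at the printed 42-day cut |
| Fluorouracil, cisplatin | 3 + 1 = 4 | 56 − 28 = 28 | inside the 15–42 class |

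Each whole day of delay was then assigned to the printed classes.

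1. **Ipilimumab.** Days 4 and 5 are on time by the column's own rule but lie in the 4–7 class. They correspond to intervals of 42 + 4 = 46 and 42 + 5 = 47 days. The other four columns have no such conflict with the 3-day rule.
2. **Overlap.** Day 42 is in both 15–42 and 42–56, in all five columns. For ipilimumab and nivolumab that day is exactly the limit, not over it.
3. **Chemotherapy limit.** Delays of 29 to 42 days are intervals of 28 + 29 = 57 to 28 + 42 = 70 days, all past 56. They share the 15–42 class with delays of 15 to 28 days, whose intervals run from 43 to 56 days.

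Protocol Section 4.5.3.2 gives the 28-day cut a further use. Its postponement rules refer to resumption on Days 9–15 and 16–29, with Day 1 the planned day, which is 8–14 and 15–28 days late. The SAP's 8–14 class matches the first band. Its 15–42 class overruns the second.

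**Other reading of the maximum row.** If 8 and 12 weeks are taken as delays, as the row label says, the >56 class isolates over-limit doses for the 8-week drugs. Ipilimumab's 84 days then falls inside >56 and cannot be separated. That reading also departs from the protocol, which counts from the previous dose. Neither reading makes the one list work in every column.

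**The case against.** Several objections are sound and limit the point.

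- **Over-limit doses.** A reader might infer that doses past the protocol's limit cannot be counted at all. The arithmetic does not support that. For ipilimumab and both nivolumab columns the limit is the 42-day cut, so over-limit doses are the top two classes once day 42 is assigned. Only fluorouracil and cisplatin are affected.
- **The word cycle.** Protocol Table 5.1-3 says of Arm B: "A cycle (4 weeks) refers to the nivolumab Q2W + FP Q4W". Taken literally, an on-time Arm B nivolumab dose would be 28 − 14 = 14 days late, and an on-time ipilimumab dose, with Arm A's 2-week cycle, would score 14 − 42 = −28. That is not a fair reading. The subtracted 42, 14 and 28 days are each drug's dosing interval, and the relative dose intensity formulas in SAP Tables 7.4.1-1 and 7.4.1-2 use the same drug-specific values. The wording merits clarification only.
- **Ipilimumab days 4 and 5.** If the 5-day rule is applied first, those doses are on time and the 4–7 class simply holds days 6 and 7. That may be the intention, but the table does not state an order, so the label conflict stands.
- **Permitted versus not permitted.** The protocol allows longer gaps for non-drug-related reasons with medical-monitor approval and, for nivolumab and ipilimumab, for steroid tapers. A 28-day cut therefore shows doses past the stated interval, not violations.
- **Nivolumab window.** The SAP's 3 days agrees with protocol Table 4.5.1.1-1. The conflict with Table 5.1-2 lies within the protocol and is not a SAP error.

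**Conclusion.** The table is wrong as written in three places: ipilimumab days 4 and 5, day 42 in every column, and the 15–42 class for fluorouracil and cisplatin. The third rests on reading the 8-week limit as an interval from the previous dose, which is how the protocol words it. The first assumes no unstated order of precedence between the table's rows. The documents do not show how many doses would be affected.

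A reader might conclude that the trial's account of tolerability is compromised. It is not. The SAP also plans relative dose intensity, doses received, cumulative dose, reasons for delay, adverse events leading to dose delay or reduction (Section 7.6.4), and a by-subject dosing listing from which intervals should be recoverable. The effect is confined to one descriptive exposure summary. This is a minor correction.

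**What to change.** These changes concern tabulation only and alter no dosing rule.

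- **Ipilimumab:** on time (≤5), 6–7, 8–14, 15–42, 43–56, >56 days.
- **Nivolumab:** on time (≤3), 4–7, 8–14, 15–42, 43–56, >56 days. For Arm A the first cut is provisional (see the last bullet).
- **Fluorouracil and cisplatin:** on time (≤3), 4–7, 8–14, 15–28, 29–42, 43–56, >56 days.
- **Maximum row:** relabel it as the longest interval from the previous dose, in line with protocol Sections 4.5.5.1 and 4.5.5.2.
- **Wording:** replace the reference to the preceding cycle's duration with the interval from the previous dose of the same drug.
- **Protocol:** reconcile the 3-day and 5-day Arm A nivolumab windows in Tables 4.5.1.1-1 and 5.1-2 before that column's on-time class is fixed. If the wider window applied, the 4–7 class would catch in-window nivolumab doses too.

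The cost is an edit to one SAP table and the reprogramming of one summary. The drawback is that the classes differ by drug, so columns are no longer directly comparable line by line.

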#### 7.4.2.2 Dose Interruptions

Each study therapy may be interrupted. This information will be retrieved from CRF dosing pages. The following parameters will be summarized by treatment arm:

• Number of subject with at least one dose infusion interrupted along with reason for the interruptions and number of infusions interrupted per subject.

#### 7.4.2.3 IV Rate Reductions

In this study, it is not allowed that IV rate is reduced.

#### 7.4.2.4 Dose Reductions

Per protocol, there will be no dose escalations or reductions of nivolumab and ipilimumab. However, for chemotherapy, dose reduction is permitted (as specified in the protocol). This information will be retrieved from CRF dosing pages.

For subjects treated with chemotherapy, the following will be summarized by treatment group:

• Number of subjects with at least one dose reduction along with the reason of the dose reduction.

#### 7.4.3 Concomitant Medications

Concomitant medications, defined as medications other than study medications which are taken at any time on-treatment (i.e. on or after the first day of study therapy and within 100 days following the last dose of study therapy), will be coded using the WHO Drug Dictionary.

The following summary tables will be provided:

• Concomitant medications (subjects with any concomitant medication, subjects by medication class and generic term).

A by-subject listing will accompany the table.

## 7.4.3.1 Subsequent Therapy

- Number and percentage of subjects receiving subsequent therapies will be summarized. Categories include:
- Immunotherapy including commercial Nivolumab (anti-PD1 agents, anti-PD-L1 agents, anti-CTLA-4 agents and others) by drug name
- Other anti-cancer agents excluding all immunotherapy (approved and investigational) by drug name
- Surgery for treatment of tumors
- Radiotherapy for treatment of tumors
- Any combination of the above

A subject listing of follow-up therapy will also be produced for subjects who had any subsequent therapy.

[figure not shown]
#### 7.5 Efficacy

## 7.5.1 Protection of Type I Error Across Primary and Secondary Endpoints

The primary and secondary endpoints are tested using the Bonferroni-based graphical approach by Maurer and Bretz (2013): see Figure 7.5.1-1 for the graphical display of the multiple testing procedure. In this graph defining the test procedure, hypotheses together with their local significance levels are represented by weighted vertices and the propagation rule is represented by weighted directed edges. Algorithm 1 in Maurer and Bretz (2013) provides the rules for updating

the local significance levels and the transition weights after rejecting an individual hypothesis. The resulting sequentially rejective testing procedure controls family-wise Type I error rate of 5% in the strong sense, and is uniquely determined by the graph in Figure 7.5.1-1.

Figure 7.5.1-1: Graphical Representation of the Testing Strategy for the Primary and Secondary Endpoints

OS = Overall survival, PFS = Progression-free survival, ORR = Objective response rate, PDL1+ = PDL1-expressing subjects, AC = all randomized subjects

In the graph in Figure 7.5.1-1, each vertex (circle) corresponds to a hypothesis to be tested. The vertices on the left hand side represent the hypotheses comparing N+I vs. CT; the vertices on the right hand side represent the hypotheses comparing N+C vs. CT. The vertices in the upper row correspond to the primary endpoints, i.e. OS and PFS in PD-L1 expressing subjects. The vertices in the rest of the rows correspond to the secondary endpoints, i.e. OS and PFS in all randomized subjects, and ORR in PD-L1 expressing and all randomized subjects. The numbers next to the vertices are the initially allocated (endpoint-specific) alpha levels. (Note that it is 0 for all secondary endpoints - meaning that they cannot be tested until alpha is passed to them from the primary endpoints.) The weight (in rectangular frame) associated with a directed edge (line)

between any two vertices indicates the fraction of the (local) significance level at the initial vertex that is added to the significance level at the terminal vertex, if the hypothesis at the tail is rejected .

The test procedure is identical for the N+I vs. CT and for the N+C vs. CT comparisons. It is as follows.

At the time of the PFS final analysis, all 4 primary endpoints will be tested, with the following initially allocated (endpoint-specific) alpha levels:

- PFS in PD-L1 expressing subjects: 0.015
- OS in PD-L1 expressing subjects: the overall initially allocated (endpoint-specific) alpha of 0.01 will be distributed over the interim analysis (IA) and final analysis (FA) based on the actual number of deaths for each comparison at OS IA, using Lan-DeMets alpha spending function with O'Brien-Fleming boundaries. (If the observed number of OS events at IA for a comparison with a given experimental arm is exactly 175 [70% of the target number of OS events], the significance levels are 0.002 and 0.009 for OS IA and OS FA, respectively.)

If none of the primary endpoints can be rejected then no secondary endpoints are tested, and the study continues to proceed to the final OS analysis. If, however, any of these endpoints can be rejected, graph will be updated as per Algorithm 1 of Maurer and Bretz (2013), and those secondary endpoints to which alpha is passed can be tested. More specifically, the algorithm ensures that in case a primary endpoint (in PDL1-expressing subjects) is rejected, its entire alpha level is passed to the corresponding (OS or PFS) endpoint in all randomized subjects. Further, if for a given experimental arm (N+I or N+C), both OS endpoints (in PD-L1 expressing subjects and in all randomized subjects) are rejected, their significance level is passed to the primary OS endpoint of the other experimental arm. For a given experimental arm, if PFS in all randomized subjects is rejected, its significance level is split into two: half of it will be passed on to the primary OS endpoint, and half of it to ORR in PDL1-expressing subjects. (Note that ORR endpoints [in PDL1-expressing and in all randomized subjects] can be tested only in case PFS in all randomized subjects is rejected.) Further, there is no direct edge between any two endpoints within all randomized subjects: this reflects the intention for any given endpoint to first give chance to the primary population to be rejected, and only thereafter for all randomized subjects.

Each time a hypothesis is rejected, and the graph is updated, the alpha levels for IA and FA will be recalculated for each remaining OS endpoint. (O'Brien-Fleming alpha spending function will be used for the primary OS endpoints [in PDL1-expressing subjects], and Pocock for the secondary OS endpoints [in all randomized subjects].)

At the time of the final OS analysis, none of the PFS or ORR endpoints will be tested. (I.e. all remaining vertices and the related edges will be deleted from the graph). For the OS analyses, all events in the database at the time of the lock will be used.

To illustrate how the sequentially rejective procedure works, a hypothetical example is included in the appendix.

The final OS analysis will be triggered when 140 events are observed among the PD-L1 expressing subjects in the chemotherapy arm. At the time of interim analysis, the significance level will be calculated according to the actual pooled events number between the treatment arm and the control arm at the interim and the estimated pooled events number between the treatment arm and the control arms at the final. At the final analysis, the significance level will be calculated using the number of events in the database at time of database lock and will consider the alpha level already spent at the interim analysis.

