Hypothesized HR after delayed effect, in non-cure subjects	0.65 in PD-L1+, 0.85 in PD-L1-	0.55 in PD-L1+, 0.75 in PD-L1-
Hypothesized median: control vs experimental	9 months* vs 12.3 months	4 months vs 5.5 months
Significance level a	0.01	0.015
FINAL ANALYSIS		
Criteria for time of LPLV	At the time of the PD-L1+ LPLV	At the time of the PD-L1+ LPLV
Projected # of events	≈514	≈512
Significance level a	[0.009] b	0.015
Power c	94%	90%
Hypothesized overall HR	0.68	0.72
Critical HR d / Minimal difference in median e	0.80 / 2.3 months	0.81 / 0.9 months
INTERIM ANALYSIS for OS		
Criteria for time of LPLV	At the time of PFS final analysis	N/A
Projected # of events	≈362 (70.4% of all events)	N/A
Significance level a	[0.002] (a)	N/A
Probability of crossing boundary c	33%	N/A
Hypothesized overall HR	0.75	N/A
Critical HR b / Minimal difference in median e	0.74 / 3.1 months	N/A
Accrual rate per month	Gradually increasing accrual rates (max = 45 subjects per months)	
Accrual Duration	29 months	

a In case the significance level from the corresponding primary endpoint is passed. (Note that endpoint-specific [i.e. initially allocated] significance level is 0.)

b For OS, significance levels will be recalculated based on the actual number of deaths at interim analysis

c Not accounting for hierarchy

d Largest observed HR at which a statistically significant difference would be observed

e Difference in median, corresponding to a minimal clinically significant effect size

\* Asia: 10 months, RoW: 6 months

Simulations were conducted in R-v3.1.3.

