Critical HR g / Minimal difference in median h	0.80 / 2.3 months	0.81 / 0.9 months
INTERIM ANALYSIS for OS b		
Criteria for time of LPLV	At the time of PFS final analysis	N/A
Projected # of events d	≈362 (70.4% of all events)	N/A
Significance level b	[0.002] e	N/A
Probability of crossing boundary f	33%	N/A
Hypothesized overall HR	0.75	N/A
Critical HR g / Minimal difference in median h	0.74 / 3.1 months	N/A
Accrual rate per month	Gradually increasing accrual rates (max = 45 subjects per months)	
Accrual Duration	29 months	

<sup>a Asia: 10 months, RoW: 6 months

b In case the significance level from the corresponding primary endpoint is passed. (Note that endpoint-specific [i.e. initially allocated] significance level is 0.)

<sup>c Results based on simulations (except: Criteria for time of LPLV)

 $^{m d}$  Projected # of events for one comparison (i.e. for N+I vs CT; and for N+C vs CT)

<sup>e For OS, significance levels will be recalculated based on the actual number of deaths at interim analysis

f Not accounting for hierarchy

Simulations were conducted in R-v3.1.3.

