- the entire significance level of the rejected hypothesis is passed to the corresponding secondary endpoint in all randomized subjects (within the N+I vs. CT comparison).

Table 10-1: Step1: Time 1, Rejection of PFS PDL1+ for N+I vs. CT

[figure not shown]
\* Nominal signifiance levels for Time 1 / Time 2, based on O'Brien-Fleming with 72% observed information fraction at Time 1

\*\* Nominal signifiance levels for Time 1 / Time 2, based on O'Brien-Fleming with 68% observed information fraction at Time 1

**Step 2**: Now assume that the secondary endpoint PFS in all randomized subjects for N+I vs. CT (shaded vertex) is significant at Time 1 at its nominal alpha. As a result, the graph is updated as follows (see also Part B in table below):

- the rejected hypothesis and its outgoing edges are removed;
- half of the rejected hypothesis' significance level is passed to ORR in PDL1-expressing subjects (secondary endpoint) and thus it can be now tested at 0.0075;
- half of the rejected hypothesis' significance level is passed to another primary endpoint, OS in in PDL1-expressing subjects and thus latter's local significance level is updated from 0.01 to 0.0175. The alpha spending function (O'Brien-Fleming with 72% information fraction at Time 1) is then re-applied to this updated local significance level.

Table 10-2: Step2: Time 1, Rejection of PFS AC for N+I vs. CT

[figure not shown]
\* Nominal signifiance levels for Time 1 / Time 2, based on O'Brien-Fleming with 72% observed information fraction at Time 1

\*\* Nominal signifiance levels for Time 1 / Time 2, based on O'Brien-Fleming with 68% observed information fraction at Time 1

Step 3: For the sake of illustration, assume that no more endpoints can be rejected at Time 1, and thus the study continues to Time 2. As the PFS and ORR endpoints were not planned to be tested at Time 2, all related vertices and edges are removed from the graph. All OS endpoints will now use the nominal significance levels for Time 2, as determined by their alpha spending functions. Assume that we can reject primary endpoint OS in PDL1-expressing subjects for N+I vs. CT (shaded vertex) at its nominal significance level of 0.0162. As a result, the graph is updated as follows (see also Part B in the table below):

- the rejected hypothesis and its outgoing edge are removed;

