- The entire local significance level of the rejected hypothesis is passed to its corresponding secondary endpoint in all randomized subjects in N+I vs. CT and thus the secondary endpoint's local significance level (across timepoints) is updated to 0.0175. The alpha spending function (Pocock with 65% information fraction at Time 1) is then applied to this updated alpha level, and it can be tested at 0.0078.

Table 10-3: Step3: Time 2, Rejection of OS PDL1+ for N+I vs. CT

\* Nominal signifiance levels for Time 1 / Time 2, based on O'Brien-Fleming with 72% observed information fraction at Time 1

\*\* Nominal signifiance levels for Time 1 / Time 2, based on O'Brien-Fleming with 68% observed information fraction at Time 1

\*\*\* Nominal signifiance levels for Time 1 / Time 2, based on Pocock with 65% observed information fraction at Time 1

Step 4: Reject OS in all randomized subjects for N+I vs. CT (shaded vertex) at Time 2. As a result:

- the rejected hypothesis and its related edges are removed;
- its entire significance level is passed to the last testable primary endpoint, OS in PDL1-expressing subjects for N+C vs. CT. Thus latter's local significance level is updated to 0.0275. The alpha spending function (O'Brien-Fleming with 68% information fraction at Time 1) is then applied to this updated alpha level, and it can be tested at 0.0257.

Table 10-4: Step4: Time 2, Rejection of OS AC for N+I vs. CT

Part A: Reject Hypothesis		Part B: Update Graph after Rejection	
N + I vs CT	N + C vs CT	N + I vs CT	N + C vs CT
0.0175 [0.0131/ 0.0078 **]	0.01 (0.0013 / 0.0096 °)  OS  PDL1  3  OS  AC		0.0275 [0.0056 / 0.0257 *]  OS  PDL1  AC

\* Nominal signifiance levels for Time 1 / Time 2, based on O'Brien-Fleming with 68% observed information fraction at Time 1

\*\* Nominal signifiance levels for Time 1 / Time 2, based on Pocock with 65% observed information fraction at Time 1 Assuming that OS in PDL1-expressing subjects for N+C vs. CT cannot be rejected, the process stops.

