- Assuming 158 PD-L1 expressing subjects randomized to the chemotherapy arm and considering the number of 102 PFS events observed so far, there would be an additional 158-102=56 subjects for whom a PFS event may still be expected per primary definition. However, per secondary definition which accounts for disease progression after subsequent therapy, a total of 135 PFS events per BICR were observed. Therefore, it is evident that for 135-102=33 subjects, PFS events per primary definition should not be expected.
- Event tracking in all randomized subjects across the three treatment arms indicated there are a total of 94 subjects are censored per primary definition due to withdrawal of consent, lost to follow-up, no scans or without PD/death after subsequent therapies. Assuming equal subject distribution across treatment arms and PD-L1 expression subgroups, it is estimated that 15 of these subjects would represent PD-L1 expressing subjects in the chemotherapy arm, thus reducing the potential pool of subjects for whom a PFS event could be expected even further.
- Therefore, among the 56 subjects without observed PFS events (per primary definition), only 56-33-15=8 subjects may contribute a PFS event per primary definition, whereas an additional 34 PFS events are needed to trigger the IA.

Based on the reasons stated above, the IA will be performed when 136 PFS events are observed or when a 12-month minimum follow-up (defined as the time from the date the last patient was randomized to the clinical cutoff date) is reached if the target number of events is unlikely to be reached among the PD-L1 expressing subjects in the chemotherapy arm. The table below provides the power based on different numbers of PFS events among PD-L1+ subjects in chemo arm using the same protocol assumption.

	Total number of PFS events for one	
PFS events among PD-	comparison (i.e. for N+I vs CT; and	
L1+ in chemo	for N+C vs CT)	Power
136	250	90%
121	218	85%
110	195	80%
100	175	75%

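### Planning figures for OS in all randomized subjects use O'Brien-Fleming spending, but the SAP tests that endpoint with Pocock

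*SAP*

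**What the plan says.** **The testing rule.** SAP 7.5.1 splits the 0.01 for OS in PD-L1 expressing subjects between interim and final "using Lan-DeMets alpha spending function with O'Brien-Fleming boundaries". It then says that the OS levels are recalculated each time the graph is updated, with O'Brien-Fleming for the primary OS endpoints "and Pocock for the secondary OS endpoints [in all randomized subjects". The final level is to be computed from the events in the locked database and "will consider the alpha level already spent at the interim analysis". Appendix 1 (Steps 3 and 4) applies the rule to all-randomized OS: local alpha 0.0175, "Pocock with 65% information fraction at Time 1", nominal levels 0.0131/0.0078.

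**The planning figures.** For the same endpoint, SAP Table 5-2 and Protocol Table 8.1-2 give:
- interim events "362 (70.4% of all events", final events about 514;
- levels 0.002 (interim) and 0.009 (final);
- interim crossing 33%, power 94%;
- critical HR and minimal median difference "0.74 / 3.1 months" at interim, and 0.80 and 2.3 months at final.

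The footnotes say that alpha must first be passed, that levels will be recalculated for the actual number of deaths, and that power and crossing probability ignore the hierarchy. None mentions a different spending function.

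**The design program.** In SAP Appendix 6, Report_results calls the boundary routine with the same argument, iuse=c(1,1), for all randomized subjects as for PD-L1 expressing subjects.

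Protocol 8.5 names only an O'Brien-Fleming type boundary, in its text on OS in PD-L1 expressing subjects. Protocol 8.4.2 leaves the rules for passing significance levels to the SAP.

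**The concern.** The two functions spend alpha in opposite ways. O'Brien-Fleming keeps most of it for the final look. Pocock at 70% information spends most of it at the interim, so the interim level exceeds the final one. The printed pair 0.002/0.009 has the O'Brien-Fleming order, and it is the pair that 7.5.1 quotes for PD-L1 expressing subjects at 175 deaths.

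This is an alpha-controlled secondary endpoint, and once both OS hypotheses of an arm are rejected, their alpha passes to the other arm's primary OS hypothesis. A reader who took the levels from the table would wrongly call a final p-value between 0.0041 and 0.009 significant, and would miss a valid interim rejection between 0.002 and 0.0079.

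**Working it through.** **Inputs** (SAP Table 5-2 and Appendix 6): two-sided alpha 0.01; 362 and 514 deaths, so t = 362/514 = 0.704; 626 subjects; delay 3/4 months, cure 15%/10% and post-delay HR 0.65/0.85 (PD-L1+/PD-L1-); control medians 10 months (Asia) and 6 months (RoW), taken from the table footnote.

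**Interim levels, two-sided**
- O'Brien-Fleming: each side spends 2[1 - Φ(z/√t)] with z = Φ⁻¹(0.9975) = 2.807. Then 2.807/0.839 = 3.345, giving 0.00082 per side and 0.0016 in all.
- Pocock: 0.01 × ln[1 + (e - 1) × 0.704] = 0.01 × ln 2.210 = 0.0079.

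**Final levels.** The final bound c₂ solves P(Z₁ < c₁, Z₂ ≥ c₂) = 0.005 minus the alpha spent per side, with correlation √t. O'Brien-Fleming: c₂ = 2.595, level 0.0095. Pocock: c₂ = 2.871, level 0.0041.

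**Check of the routine against Appendix 1.** Pocock, alpha 0.0175, t = 0.65: 0.0131/0.0078. O'Brien-Fleming, alpha 0.0275, t = 0.68: 0.0056/0.0257. O'Brien-Fleming, alpha 0.0175, t = 0.72: final 0.0162. All match.

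**Power and crossing.** The Appendix 6 model was simulated in two separate runs of 10,000 trials each, with 363 and 515 deaths on average. The program defines the critical HR as the largest HR among significant simulated trials, and the minimal median difference as control median × (1/critical HR - 1). The control median is taken as 9 months here.

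| OS, all randomized (interim/final) | Printed | O'Brien-Fleming | Pocock |
|---|---|---|---|
| Level | 0.002 / 0.009 | 0.0016 / 0.0095 | 0.0079 / 0.0041 |
| Interim crossing | 33% | 33% | 51-52% |
| Power at final | 94% | 94-95% | 91% |
| Critical HR, simulated | 0.74 / 0.80 | 0.74 / 0.80 | 0.77 / 0.78-0.79 |
| Median difference, months | 3.1 / 2.3 | 3.2 / 2.2-2.3 | 2.6-2.7 / 2.4-2.5 |

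For example, under Pocock 9 × (1/0.774 - 1) = 2.6 and 9 × (1/0.780 - 1) = 2.5. In closed form, exp(-2c/√d), the Pocock boundary HRs are exp(-2 × 2.655/√362) = 0.756 and exp(-2 × 2.871/√514) = 0.776.

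O'Brien-Fleming reproduces the printed figures to within rounding and simulation error; Pocock does not.

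**Other settings under Pocock**
- Appendix 7 also allows the interim "or when a 12-month minimum follow-up" is reached. Assuming 29-month accrual, that puts it at about 41 months, with 460 of 515 deaths (t = 0.893): levels 0.0093/0.0041, about 85% interim crossing, 91-92% power.
- In Appendix 1 Step 2 the primary OS "local significance level is updated from 0.01 to 0.0175". If 0.0175 is passed on at t = 0.704, the levels are 0.0139/0.0076.

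**The case against.** The best defence is that the printed levels will never be used. They are bracketed, conditional on alpha being passed, and flagged for recalculation, while 7.5.1 and Appendix 1 give the full operative rule. A statistician executing the SAP would apply Pocock.

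The endpoint is also gated. It can be tested only after OS in PD-L1 expressing subjects is rejected, which at the interim has probability 29%, so neither 33% nor 51% is attainable. In a 6,000-trial run with the gate, interim rejection was about 19% under O'Brien-Fleming and 25% under Pocock, and overall rejection about 88% and 85%. The final critical HR and median difference barely move.

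Much of this stands: the practical effect is modest, and the replacement HRs and median differences vary a little with the seed and the definition used. It does not remove the mismatch. The footnote on deaths cannot explain it, because at exactly 70.4% information Pocock still gives 0.0079/0.0041, with the order reversed. The tables state that they ignore the hierarchy, so the ungated comparison is like for like, and the gated power also falls by about 3 points.

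**Conclusion.** The concern holds. The tabulated OS levels, crossing probability, power and critical HRs for all randomized subjects are arithmetically right for O'Brien-Fleming, but they do not describe the test that the SAP specifies. The final level is overstated about 2-fold (0.009/0.0041 = 2.2). The interim level is understated about 4-fold as printed (0.0079/0.002), or about 5-fold unrounded (0.0079/0.0016). Power is overstated by about 3 points and stays near 91%.

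The effect is confined to planning figures. Type I error is controlled if 7.5.1 is followed, and the sample size and triggers rest on the PD-L1 expressing population. The figures assume that alpha 0.01 is passed, 70.4% information and the Appendix 6 survival model. The reading of iuse=c(1,1) as O'Brien-Fleming rests on its shared use with the PD-L1 analysis and on the match of the output.

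**What to change.** Keep Pocock, which the SAP states in 7.5.1 and works through in Appendix 1. Then:

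1. Rerun Appendix 6 with Pocock spending for the all-randomized OS analysis only.
2. Restate the OS rows of SAP Table 5-2 and Protocol Table 8.1-2: levels about 0.0079/0.0041, interim crossing about 51%, power about 91%. Take the critical HRs and median differences from the rerun; the values above show what to expect.
3. Add a footnote that SAP 7.5.1 governs and that the levels depend on the actual information fraction and the alpha passed. The 12-month trigger can serve as an illustration (about 0.0093/0.0041 at about 89% information), labelled as an assumption.

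The cost is one changed program argument, one rerun, two table corrections and a footnote. The Protocol table must be corrected by amendment or administrative letter under Protocol 9.1.1. The test does not change. The one downside for the sponsor is that the stated power reads about 91% instead of 94%.
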